13.0 Regulatory Requirements

13.1 Informed Consent

- Written consent will be obtained in the CCTC CRC during the screening visit after the volunteer has successfully completed an initial phone screening. Each member of the research team is designated to administer the informed consent. Each research team member has been trained by the PI in administering informed consent and has completed CITI and HIPAA training as required by IRB.
- Each volunteer will receive a copy of the signed informed consent document (ICD) for his/her records. The study copy of the signed ICD will be stored in the subject's study binder in a locked file cabinet in the PIs locked office. Each member of the study team has access to these study binders. Because they are stored in the PI's office, the PI will supervise access.

13.2 Subject Confidentiality

- Subject's confidentiality will be maintained by using unique identifiers and keeping source documents with sensitive subject information in protected environments as described above. Further, all research team members are Collaborative Institutional Training Initiative (CITI) and HIPAA trained.
- All research team members have access to the study data that will be stored digitally on a secure database. Study data are kept separate from source documents containing sensitive subject information. Source documents such as initial screening forms, informed consent and other data sheets containing dates are kept in subject binders in a locked cabinet in the PI's office. Security standards will include 2 locked doors for paper records, and 2 electronic signatures for electronic data (i.e. main computer, then specific access to data files). The PI will oversee who has access to these files.
- Upon subject enrollment, the subject is assigned a unique identifier. This unique identifier will be used for all data sheets and data spreadsheet entries. Only the initial screening form, the informed consent and the identifier key will contain direct identifiers.
- The research team will request access to participant's PHI through a patient authorization document, which if signed by the subject will give the researcher permission to use PHI collected during the research study for defined purposes.
- After study completion, we plan to scan all source documents into electronic format for long term storage on an Academic Computing and Communications Center (ACCC) protected UIC server that only the PI can access. Upon verification of electronic transfer, original source documents will be shredded and disposed of into confidential file disposal bins.
- Sensitive subject information such as personal identifiers are required to determine subject eligibility and required to contact the individual for study visits. Once the subject is enrolled, the subject is assigned a unique identifier and these initial source documents are no longer needed for the successful completion of the study. The steps above describe the handling of these source documents.
- A *Certificate of Confidentiality* is not required, as the information collected if disclosed would not significantly harm or damage the participant.

13.3 Unanticipated Problems

- Based on the low level of risk during study participation, serious adverse events are unlikely to occur. Discomfort during the blood draws will be most likely problem that could occur during participation. Every effort will be made to provide comfort to participants whenever possible. Should participants experience discomfort or emotional upset from any of the research procedures, they will be reminded that they are under no obligation to participate in the study, and can withdraw consent and discontinue participation at any time without prejudicing their current or future relations with UIC or UI Health, or its physicians. Students or employees will be reminded that participation or nonparticipation in the study will not affect current or future medical care at UIC or the UI Health and/or position of employment or course of studies in these institutions.

- Additional potential problems such as breach of confidentiality and emotional upset may also occur. Every effort will be made to maintain subject confidentiality using the data management procedures described above. In the event of breaches or suspected breaches of data security, including sensitive information, an unanticipated problem will be reported to the IRB using the Event Requiring Prompt Reporting form within 5 working days of becoming aware of the event. Possible data breaches include, but are not limited to, the following: lost or misplaced files/folders, improper disposal of paper containing sensitive information, loss/violation of the integrity of decryption key or process.
- A participant's study will be stopped in the event she requests not to continue, or if she has a reaction to any procedure, the ingestion of the glucose beverage during the OGTT, the HCG injection, dairy cream ingestion during the CCT, difficulty obtaining a peripheral intravenous line, administration of salsalate (i.e. allergies, persistent or serious side effects, unusual anxiety). In the unlikely event that a serious side effect occurs, the participant will immediately be referred for further evaluation and treatment. All participants will be assessed for side effects at the end of the study and any discussions will be documented within each participant's study binder. Follow-up with the IRB or CRC will also be noted, and copies will be kept of all correspondence.
- A participant will be withdrawn from the study if she fails to comply with any of the research procedure, if the study is stopped for an unforeseen reason, or in the event of physical injury or illness resulting from the research procedures. Failure to take the appropriate dose of medication not related to downward dose titration for expected symptom control can result in withdrawal of a subject from the study. The degree of noncompliance with medication use that can have a significant adverse impact on the study may vary from subject to subject and the decision to withdraw a subject for medication use noncompliance will be left to the discretion of the investigator.
- The study will be completely suspended in the extremely unlikely event of death of a subject, or at the moment it becomes apparent that any particular serious side effect is occurring at an unanticipated increased frequency.
- The PI will keep abreast of scientific reports or therapeutic development, and results of related studies that impact subject safety; and will inform subjects immediately of new information from these reports or studies that change the risk/benefit ratio that might cause them to change their mind about continued participation. This type of information will also be reported to the DSMB and to the IRB during an annual continuing review. Participants will be instructed to notify the principal investigator or his designee as soon as the desire to withdraw is apparent. The circumstances related to the request to withdraw will be reviewed to determine the necessity of performing a post-study evaluation to insure safety.

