Interim Meetings: In open session, the DSMB will meet at least twice a year to review the ongoing recruitment process, participant withdrawal and protocol deviations. It will review any study protocol amendments and follow the continuing review process. It will review participant safety and discuss any serious adverse events that may occur, including the relationship of adverse events to study intervention. It will review the study protocol to determine if any protocol revisions are merited as suggested by interim results, adverse events, or external events such as new FDA recommendations. It will review the informed consent document and confirm consistency with risks of participation to determine if any consent document revisions are merited. It will discuss any issues raised by the clinical study team. At the conclusion of each meeting, one of the following dispositions will be recommended: continue the study without changes, continue the study with specified changes, place the study on Clinical Hold pending further discussion or investigation, or terminate the study.

Key Features to be Assessed: Monthly salicylate levels measured at Visits 1, 6, 7 and 8 by Labcorp Clinical Laboratories will eventually be used to assess compliance after the study is unblinded upon its completion to accurately interpret the study data, but will not be used for clinical management. To avoid blinding bias, the monthly salicylate levels will not be posted in a subject's electronic medical record. Instead, DSMB members under [name] direction will prospectively receive copies of these salicylate levels for safekeeping. Development of tinnitus during salsalate use will be used to assess salicylate toxicity clinically as in a previous large multicenter trial.¹⁹ As an additional precaution, salsalate will be prepared as 500 mg capsules and identical placebo capsules so the blinding will not be jeopardized when changing the dose in one capsule increments to manage tinnitus.

Operating Procedures: The DSMB will convene after 5 participants have completed the study protocol or 6 months following completion of the first participant (whichever occurs first); and thereafter at least twice a year. If there is a concern about serious adverse events, more frequent meetings may be called by vote. If unexpected and/or serious adverse events occur disproportionately to what may be anticipated, the study will be placed on clinical hold and the IRB will be consulted for guidance.

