- A participant's study will be stopped in the event she requests not to continue, or if she has a reaction to any procedure, the ingestion of the glucose beverage during the OGTT, the HCG injection, dairy cream ingestion during the CCT, difficulty obtaining a peripheral intravenous line, administration of salsalate (i.e. allergies, persistent or serious side effects, unusual anxiety). The participant's treating physician will attend to any serious adverse events that may occur until they have resolved or refer the participant to the appropriate provider as needed. A participant will also be asked to stop the study if she is not compliant with the requirements of the study protocol. All participants will be assessed for side effects at the end of the study. Study discussions will be documented within each participant's study binder. Follow-up with the IRB or CCTS CRC will also be noted, and copies will be kept of all correspondence.
- If a participant withdraws from the study, she will be replaced by a different participant to achieve accrual of 90 participants to complete the study. Additional reasons for withdrawal may include but are not limited to a family emergency, a new medical diagnosis, participant preference or development of any persistent study medication side effects that do not resolve with common clinical measures in a timely fashion. The IRB and CCTS CRC will be notified during an annual continuing review of subject accrual to date, and any withdrawals or dropouts.
- If a serious adverse event occurs during the study, the PI will promptly report the event to the IRB (in accordance with UIC OPRS Prompt Reporting policy) and to the study DSMB for review and possible action. In the unlikely event of any serious adverse reactions occurring during this study, the DSMB will also provide appropriate clinical expertise for advice and assistance. The study will be completely suspended in the event of death of a subject.
- The PI will keep abreast of scientific reports or therapeutic development, and results of related studies that impact subject safety; and will inform subjects immediately of new information from these reports or studies that change the risk/benefit ratio for study participation. This type of information will also be reported to the DSMB and to the IRB during an annual continuing review.

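### Outside information that changes the risk/benefit ratio goes to subjects at once, but its report to the DSMB and IRB is tied to an annual review; this conflicts with the DSMB's twice-yearly remit, and the protocol writes no prompt route.

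*Combined protocol and SAP*

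**What the plan says.** Near the end of section 11.0 (Data and Safety Monitoring), the PI undertakes to follow the literature and related studies and "will inform subjects immediately of new information from these reports or studies that change the risk/benefit ratio for study participation". Section 13.3 (Unanticipated Problems) repeats this almost word for word: the PI "will inform subjects immediately of new information from these reports or studies that change the risk/benefit ratio". In both places the sentence on the oversight bodies is the same: "This type of information will also be reported to the DSMB and to the IRB during an annual continuing review".

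Section 11.0 also describes the DSMB's work. Under Interim Meetings, "In open session, the DSMB will meet at least twice a year to review the ongoing recruitment process", among other tasks. At these meetings it decides "if any protocol revisions are merited as suggested by interim results, adverse events, or external events such as new FDA recommendations". It also checks that the consent document still matches the risks, takes up matters raised by the study team, and ends with a recommendation that may be a clinical hold or termination. Under Operating Procedures, "The DSMB will convene after 5 participants have completed the study protocol or 6 months following completion of the first participant", whichever comes first, and at least twice yearly after that. The DSMB chair's report goes to the IRB within six weeks of each meeting.

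**The concern.** The protocol treats this information as serious enough to tell every subject without delay. The bodies that can recommend a hold (the DSMB) or approve a revised consent form (the IRB) are assigned a yearly report. The DSMB is also asked to weigh external events and consent accuracy at least twice a year, and the protocol does not say how the PI's information is to reach those meetings. Someone following the reporting sentence literally could let a DSMB meeting pass without putting forward information that subjects already have.

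What is at stake is the timing of independent oversight. While the information is outstanding, enrolment into a treatment period of 11 to 13 weeks could continue without either body having judged whether the trial or its consent form should change. No endpoint, analysis or estimate is affected.

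**Working it through.** The plan gives no figure to reproduce. The check compares the stated intervals and then looks for a faster route elsewhere in the text.

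**Inputs**

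- Notice to subjects: immediate (sections 11.0 and 13.3).
- PI's report to the DSMB and IRB: at the annual continuing review (same two places).
- DSMB meetings: at least two a year (section 11.0).
- First interim DSMB meeting: after 5 completers, or 6 months after the first completer, whichever is earlier (section 11.0).
- DSMB report to the IRB: within six weeks of a meeting (section 11.0).
- Treatment: about 12 weeks, range 11 to 13 (section 6.0).

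**Intervals**

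1. *PI directly to the IRB.* If the information arises just after an annual review, the wait is up to about 12 months. The same applies to the DSMB if the annual timing governs both bodies named in the sentence.
2. *Through the DSMB.* Two meetings a year, assumed evenly spaced, are 12 / 2 = 6 months apart, so the wait for the DSMB is up to about 6 months. Adding six weeks for its report (6 / 52 × 12 = 1.4 months) gives 6 + 1.4 = 7.4, or about 7.5 months to the IRB. The text fixes no spacing, so uneven meetings would lengthen the longest gap.
3. *Start of the trial.* Before the first interim meeting the DSMB gap can be longer. About 12 weeks to the first completion (12 / 52 × 12 = 2.8 months) plus 6 months is 8.8, or about 9 months from the start of treatment of the first subject to complete. It is shorter if five subjects finish sooner.

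**Search for a prompt route in the protocol**

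| Place | What it covers | Outside information? |
|---|---|---|
| 11.0, prompt reporting to IRB and DSMB | Serious adverse events arising in this study | Not stated |
| 13.3, report within 5 working days | Breaches of data security | No |
| 11.0, extra DSMB meetings by vote | Concern about serious adverse events | Not named |
| 11.0, PI's interim reports to the DSMB | Baseline data, recruitment, withdrawals, adherence, deviations, adverse events | Not listed |
| 11.0, list of monitored items | Includes results of related studies bearing on safety | Yes, but no timing or recipient |

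No row gives a time limit for outside information to reach either body. The DSMB is to consider changes "suggested by interim results, adverse events, or external events such as new FDA recommendations", but the list of reports it receives does not include that material.

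**The case against.** The strongest reply is that the sentence names an occasion for reporting and does not exclude earlier notice. A reader might infer that the DSMB and IRB hear of such information only once a year; the word 'only' is not in the text. The annual timing can also be read as attaching to the IRB alone, since yearly re-approval is an IRB process. On that reading no annual delay to the DSMB is stated, and its meetings already cover external events and study-team issues. This stands, and it is why the DSMB interval is given as about 6 months under the meeting schedule and not as a year. It does not remove the conflict: the sentence names both bodies before a single timing phrase, and an ambiguous safety-reporting rule still needs settling.

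A reader might also infer that the consent form cannot be revised before the annual review. The documents do not support this. Nothing confines amendments to that review, and section 5.0 requires a meeting with each volunteer to explain the risks. Nor does the text limit extra DSMB meetings to serious adverse events: it sets a minimum frequency and names that concern as one ground.

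Section 11.0 refers to an institutional prompt-reporting policy for serious adverse events. The policy may cover outside information too, but its scope is not in the documents. The absence of a prompt route can therefore be asserted for the protocol text alone.

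Finally, enrolled subjects are told at once and may withdraw, so their main protection does not wait for either body. That is correct and limits the harm, but it does not replace independent review of whether enrolment should continue unchanged.

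**Conclusion.** The point holds as a conflict in the written reporting rule. Sections 11.0 and 13.3 set annual reporting to the DSMB and IRB, section 11.0 expects the DSMB to review external events at least twice a year, and the protocol sets no prompt route to either. The possible delay is up to about 12 months for the PI's direct report to the IRB. Through the DSMB it is about 6 months to that board and about 7.5 months to the IRB, assuming even spacing and that the information is in fact put to the next meeting. The gap before the first interim meeting may be longer.

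These are the longest intervals that the text permits. It would be tempting to turn them into a share of women who finish treatment before oversight hears of the information. That would require a distribution for when information arises and the harshest reading of the sentence; the documents supply neither, so no such figure is given. The change is worth making because the rule concerns subject safety and appears in two places.

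**What to change.** In both section 11.0 and section 13.3, replace the annual timing with wording such as: *Such information is reported to the DSMB chair and the IRB at the same time as subjects are informed, and is summarised again at the annual continuing review.* Under Operating Procedures in section 11.0, add receipt of such a notice as a further ground for calling an extra DSMB meeting.

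The cost is one sentence in two places, one added clause, and an occasional extra notice or meeting. Data, sample size and study procedures are unaffected.
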